### 13.3 Description of the Analyses

- **Safety Analysis:** All safety data will be summarized with descriptive statistics (number of subjects [N], mean, standard deviation [SD], median, minimum, and maximum) for continuous variables, and frequency and percentage for discrete variables. The safety summary will include AEs, serious adverse events (SAEs), clinical laboratory data, vital signs, physical examination, and ECG data. All individual subject data will be listed by subject.
- **Efficacy Analysis:** The primary analysis compares the proportion of subjects with a  $\geq 50$  % change in AEC at 12 weeks in the 2 randomized arms. If there is dropout, the primary analysis will be the intent-to-treat analysis, which includes all subjects who received the Day 0 treatment. We will compare with a one-sided Fisher's exact test at the 2.5% level of significance, or equivalently a two-sided central Fisher's exact test at the 5% level.
- For the secondary analysis comparing the 2 groups on the post-treatment AEC at 12 weeks as a percentage of the pre-treatment AEC, we use a Wilcoxon-Mann-Whitney test.
- There are other secondary endpoints with continuous responses that measure a change from pre-treatment to after 12 weeks of treatment: for example, % bone marrow eosinophils, and % bone marrow myeloid precursors. These will be analyzed similarly to the percentage of pretreatment AEC.
- As exploratory analyses, we may use a Mixed-Effect Model Repeated Measure (MMRM) model to analyze changes in AEC over time. The dependent variable will be the percentage of baseline AEC at post-baseline protocol-specified visits (up to the 12 week visit). Treatment group will be fitted as the explanatory variable, together with visit, the interaction between visit and treatment. Visit will be fitted as a categorical variable, and the variance-covariance matrix will be assumed to be unstructured. If the procedure does not converge, then a compound symmetric variance-covariance matrix will be used instead.
- **Calculation or derivation of pharmacokinetic variables**  
The PK analyses will be performed at (or under the guidance of) AstraZeneca Research and Development.

Due to the limited sampling schedule, the PK assessment will be primarily based on the observed steady-state serum trough (predose) concentrations,  $C_{trough}$ . Empirical evaluation of potential impact of demographic covariates and ADA on  $C_{trough}$  will be conducted. Serum concentrations of benralizumab, summary statistics, empirical covariate analysis results and PK profiles will be provided in a clinical PK report (an addendum to the CSR).

To further characterize the pharmacokinetic properties of benralizumab in HES, the PK data will be merged with those from other clinical studies for a population-based, which will be presented in a separate pharmacometrics report outside of the CSR.

- **Calculation or derivation of immunogenicity variables**

ADA assessments will be conducted utilizing a tiered approach (screen, confirm, titer). Evaluations will be made at baseline (prior to benralizumab administration), and at specified time points during the treatment and follow up phases of the study or discontinuation. ADA titers by treatment group and visit will be summarized. The association of ADA status (positive or negative) with treatment-emergent adverse events (TEAEs)/ treatment-emergent serious adverse events (TESAEs), benralizumab concentration and blood eosinophil levels will be evaluated. In addition, the association of ADA titers ( $\geq$ median titer vs.  $<$  median titer) with TEAEs/ TESAEs, benralizumab concentration and blood eosinophil levels will be evaluated for ADA positive subjects only.

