#### Safety.

Results of the AstraZeneca-sponsored asthma studies (Studies MI-CP158, MICP166, MI-CP186, MI-CP197, and MI-CP220) showed no emerging safety findings. As reflected in the analysis of study MI-CP220, a placebo controlled study of sc multiple dose benralizumab in 609 adults with asthma, treatment-emergent adverse events (TEAE),

regardless of causality, occurred at an approximate 10 percentage point higher frequency in the combined benralizumab group compared with the placebo group with events classified as Infections, General Disorders and Administration Site Conditions, and Musculoskeletal and Connective Tissue Disorders largely accounting for this difference.

Treatment-emergent adverse events within each of these classifications that occurred at least 5 percentage points higher in the combined benralizumab group than in the placebo group were as follows:

- Infections: Nasopharyngitis, upper respiratory tract infection, and pharyngitis
- General Disorders and Administration Site Conditions: Asthenia, contusion, hypotension, injection site erythema, injection site reaction, and pyrexia
- Musculoskeletal and Connective Tissue Disorders: Muscle spasm and pain

Treatment-emergent adverse events classified as Respiratory, Thoracic, and Mediastinal disorders were the most frequently occurring in both the placebo and combined benralizumab groups, with asthma being the most frequently occurring TEAE.

No apparent dose response on the incidence of TEAEs was observed across the individual benralizumab dose groups. The majority of these TEAEs were mild or moderate in severity. Severe TEAEs, regardless of causality, occurred in 20/221 subjects (9.0%) in the placebo group and 47/385 subjects (12.2%) in the combined benralizumab group.

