### 2.2 Secondary Objectives

The secondary objectives will be:

- 1) To assess the safety of sc benralizumab in reducing eosinophilia in subjects with HES
- 2) To assess the effect of benralizumab on end organ manifestations of HES
- 3) To investigate the effects of benralizumab on bone marrow eosinophils, mast cells and their precursors
- 4) To assess the long-term safety and efficacy of sc benralizumab in reducing eosinophilia in subjects with HES
- 5) To assess the pharmacokinetics of benralizumab and the development of ADA levels in HES
- 6) To assess the efficacy of every 8 week dosing of benralizumab in HES

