## 3 Study Design

### 3.1 Description of the Study Design

This study will be a single center trial with 5 parts: 1) randomized, double-blind sc benralizumab vs. placebo every 4 weeks for 12 weeks, 2) open-label sc benralizumab every 4 weeks for 12-36 weeks, 3) open-label sc benralizumab extension for benralizumab responders, with doses every 4 weeks for 6 months, 4) open label substudy of sc benralizumab administration every 8 weeks in complete responders, and 5) open-label extension of self-administered sc benralizumab using an autoinjector for subjects with a sustained and complete response, for a minimum of 2 years. Eligible subjects enrolled on study protocol 94-I-0079 (Activation and function of eosinophils in conditions with blood or tissue eosinophilia) or referred from outside physicians for evaluation of hypereosinophilia will be invited to participate. A maximum of 20 subjects will be enrolled.

Baseline evaluation will include a complete history and physical examination, routine laboratory testing and assessment of end organ involvement (see [Appendix A](#)). Baseline research studies will include bone marrow aspirate and biopsy to assess eosinophil and mast cell numbers and activation, storage of peripheral blood mononuclear cells (PBMC) for future studies, assessment of baseline eosinophil activation and T/B/NK subsets by flow cytometry, and measurement of serum markers of eosinophil and mast cell activation. Potential predictors of response to benralizumab, including eosinophil surface and soluble IL-5R $\alpha$  levels and plasma cytokine profiles, will also be explored.

Part 1: Benralizumab (30 mg) or placebo will be administered sc every 4 weeks for 3 doses (at weeks 0, 4 and 8). Eosinophil counts will be blinded during this time and background HES therapy will not be tapered.

Part 2: Following the placebo-controlled portion of the trial, all subjects will receive an sc injection of benralizumab at weeks 12, 16, and 20. Eosinophil counts will be unblinded after the first week of open-label therapy (study week 13) and HES therapy may be tapered if clinically indicated. Subjects demonstrating a response at the 24 week visit (eosinophil count <1000/ $\mu$ L and stable or improved clinical symptoms without an increase in background HES therapy) will receive additional 30 mg sc injections every 4 weeks for 6 doses. Non-responders will receive no further doses of benralizumab.

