Appendix F: FASENRA PEN: Instructions for Use).

### **5.3.2 Study Drug Dosing**

Population modelling of clinical efficacy endpoints (Asthma Exacerbation Rate (AER), Asthma Control Questionnaire (ACQ), and Forced Expiratory Volume in 1 second (FEV1)) from the interim analysis for the Phase 2 asthma study, MI-CP220, and stochastic simulations identified the optimal dose and regimen for the pivotal Phase 3 studies with benralizumab in adult subjects with asthma as 30 mg every 4 weeks for 3 doses then every 8 weeks thereafter. This dosing regimen corresponds to the ED90 for AER and ACQ, and maintains a steady-state PK exposure close to EC90 levels for FEV1 and ACQ. With a steady-state PK exposure 50% higher than 20 mg every 8 weeks, the 30 mg dose every 8 weeks is expected to reduce the impact of PK variability related to factors such as higher body weight. The incidence of ADA (especially high-titer ADA) and the impact on PKPD were dose-dependent with decreased incidence and impact at higher doses. However, the ADA response was not more frequent in those subjects with blood eosinophils  $\geq 300$  cells/ $\mu$ L (20.7%) as compared to those with blood eosinophils  $< 300$  cells/ $\mu$ L (21.7%). Since doses higher than 20 mg are expected to reduce the impact of ADA without modifying the dose interval, and there are no identified safety risks that would warrant consideration of a lower dose, subjects will receive 30 mg every 4 weeks for 3-12 doses depending on whether they receive drug or placebo during the first part of the study and whether they demonstrate a clinical and hematologic response at study week 24.

Subjects who complete the study and for whom benralizumab appears to provide a sustained clinical benefit, may be eligible to receive drug under an open-label extension until regulatory approval and commercial availability of the marketed drug to prescribing physicians (for HES), or until AstraZeneca ceases development of benralizumab for this indication. Complete responders may be eligible to extend the dosing interval to every 8 weeks after sustained and complete remission of eosinophilia for  $\geq 2$  years at the investigator's discretion.

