## **6.4 Study Phase**

Within 14 days of completion of baseline studies, subjects will begin treatment with study drug.

Benralizumab (30 mg) or placebo will be administered sc (as described in Section 5.4) in the OP11 clinic, the 5 SW Day Hospital, or the 5 SE inpatient nursing unit. Vital signs will be checked immediately prior to and at 30 minutes after the injection.

Subjects will be admitted to the inpatient ward for overnight observation following the first dose of study drug to facilitate monitoring of AEs. The inpatient stay may be extended if clinically indicated. Subjects will be seen daily (in OP11 or on the inpatient ward) for 3 days following the first dose of study drug, and then at weeks 1, 2, 3, 4, 6, 8, 10, and 12. Re-dosing of benralizumab or placebo will occur every 4 weeks for a total of 3 doses (at weeks 0, 4, and 8). Subjects who develop AEs after the first dose of study drug may be monitored during subsequent doses at the discretion of the investigator. Subjects who develop grade 3 or greater AEs that are considered by the investigator to be possibly, probably, or definitely related to study drug will promptly, and prior to subsequent dosing, be discussed in writing or verbally with a Sponsor Medical Monitor in the Clinical Safety Office.

At the 12 week visit, all subjects will receive benralizumab (30 mg) sc. Since the subjects who received placebo during the first 12 weeks of the study will be receiving their first dose of benralizumab at this visit, all subjects will be admitted to the inpatient ward for overnight observation following the first dose of study drug and followed daily (in OP11 or on the inpatient ward) for 3 days, every week for 4 weeks and then at weeks 1, 2, 3, 4, 6, 8, 10, and 12, 13, 14, and 15. Re-dosing of open-label benralizumab will occur every 4 weeks for a total of 3 doses (at weeks 12, 16 and 20), after which subjects demonstrating a clinical response will continue to receive additional doses every 4 weeks for one year. Non-responders will receive no further doses of benralizumab. Subsequent visits will occur at 4-week intervals for responders and at 12-week intervals for non-responders for the duration of the study. After a minimum of 2 years of complete response on the open-label extension, the dosing interval (and visits) may be increased to every 8 weeks (the FDA-approved dosing interval for severe eosinophilic asthma).

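### Adverse events are summarised by frequency and percentage with no exposure denominator, on-drug window or period split, so long-term percentages depend on time on drug and week-12 first-dose reactions could be counted under placebo

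*Combined protocol and SAP*

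**What the plan says.** - **Summary scale.** Section 13.3 (Safety Analysis) puts all safety data under descriptive statistics, with "and frequency and percentage for discrete variables". It adds that "All individual subject data will be listed by subject". The only other adverse event (AE) analysis there is "The association of ADA status (positive or negative) with treatment-emergent adverse events", with a parallel one by titer. No exposure-adjusted rate, person-time denominator, on-drug window or tabulation by period is given. Treatment-emergent events are mentioned but not defined.
- **Objective.** Section 2.2 includes "To assess the long-term safety and efficacy of sc benralizumab in reducing eosinophilia in subjects with HES".
- **Exposure.** Section 5.3.2 says "subjects will receive 30 mg every 4 weeks for 3-12 doses depending on whether they receive drug or placebo during the first part"; week-24 response is the other determinant. Section 3.1 says week-24 responders "will receive additional 30 mg sc injections every 4 weeks for 6 doses", while non-responders get none. Responders may then enter an open-ended extension.
- **Follow-up.** Section 6.4: "Subsequent visits will occur at 4-week intervals for responders and at 12-week intervals for non-responders for the duration of the study". Section 11.2 elicits AEs at each contact.
- **Recording period.** Section 11.2 ends AE recording at the 1-year follow-up. Section 6.5 and Appendix B keep AE assessment in visits after week 48.
- **Safety cut.** Section 11.13.1 analyses safety data through the 13-week visit. Section 6.4 gives every subject open-label benralizumab at week 12.
- **First-dose reactions.** Appendix D (item 5) describes fever, nausea, fatigue and myalgia 4 to 6 hours after the first double-blind or first open-label dose in some subjects, and not after other injections.

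**The concern.** Scheduled exposure is equal in the randomised 12 weeks, so percentages suit that comparison. They do not suit the long-term objective on their own. The share of subjects with at least one event grows with observation time even when the event rate is constant and the drug does nothing. Subjects here differ in time on drug by design. Week-24 non-responders also stay under observation after their last dose, with contacts a third as frequent as responders'.

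A long-term benralizumab percentage read beside 12 placebo weeks would show an excess from duration alone. The scale of interest is small: section 1.1.3 reports that treatment-emergent events in the large asthma study "occurred at an approximate 10 percentage point higher frequency in the combined benralizumab group compared with the placebo group".

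The second problem is the cut-off. A placebo-arm subject who reacts within hours of the week-12 injection does so inside a data cut that runs to week 13. Unless the tables attribute events by drug actually received, a reaction to benralizumab can be counted as a placebo event.

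**Working it through.** **1. Reproduce the dose range.** Sections 3.1 and 6.4 give three blinded doses (weeks 0, 4, 8), three open-label doses (weeks 12, 16, 20) and six more for responders.

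| Arm, week-24 status | Active doses | Weeks on drug by week 48, at 4 per dose |
|---|---|---|
| Benralizumab, responder | 3 + 3 + 6 = 12 | 48 |
| Benralizumab, non-responder | 3 + 3 = 6 | 24 |
| Placebo, responder | 3 + 6 = 9 | 36 |
| Placebo, non-responder | 3 | 12 |

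This matches the 3 to 12 doses in section 5.3.2. The spread is 48/12 = 4-fold.

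**2. Effect of exposure length alone.** The documents give no AE rate for this population, so the rates r below are assumptions. With a constant rate and no drug effect, P(at least one event) = 1 − exp(−r × weeks/52).

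| r per person-year | 12 weeks | 48 weeks |
|---|---|---|
| 0.1 | 2.3% | 8.8% |
| 0.5 | 10.9% | 37.0% |
| 1.0 | 20.6% | 60.3% |

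For example, 1 − exp(−0.5 × 12/52) = 10.9% and 1 − exp(−0.5 × 48/52) = 37.0%.

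**3. If AEs are recorded in the extension.** Two extension years (assumed) bring the longest exposure to 48 + 104 = 152 weeks, or 152/12 = 12.7 times the shortest. The same formula then gives 25.3%, 76.8% and 94.6%. If section 11.2 governs, these figures do not apply and the 4-fold spread is the relevant one.

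**4. Direction of the off-drug effect.** Assume 50% responders in each arm, so 5 subjects in each of the four groups, and an on-drug rate of 0.5. Follow each subject from first active dose to week 48: on/off-drug weeks are 48/0, 24/24, 36/0 and 12/24. With off-drug rate m, each group's percentage is 1 − exp(−(0.5 × on + m × off)/52), and the pooled figure is the mean of the four.

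| m per person-year | Pooled percentage with an event |
|---|---|
| 0 | 24% |
| 0.25 | 29% |
| 0.5 | 33% |
| 1.0 | 40% |

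Had all 20 had 48 weeks on drug, the figure would be 37%. The pooled value can fall on either side of it.

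**5. The week-12 cut.** Part 2 starts with the week-12 injection (section 3.1). Reactions follow the first active dose by 4 to 6 hours (Appendix D). The safety cut is the 13-week visit (section 11.13.1). The interval from the week-12 injection to week 13 is active-drug time for every subject, including those randomised to placebo. With 10 per arm, one misattributed subject moves an arm's percentage by 1/10 = 10 percentage points.

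**The case against.** The strongest reply is that the plan leaves the long-term layout unspecified; it does not prescribe a wrong one. Frequency could mean events as well as subjects. No section says that periods will be pooled or that extension percentages will be set beside placebo. Section 13.4 ties the first analysis to data from the first part of the study, which can be read as stopping at week 12. Safety is descriptive, all data are listed, and the DSMB reviews twice a year. Rates could be derived later from dose and AE dates. They would also be imprecise: with 50% to 90% responders (assumed), off-drug time to week 48 is 240/52 = 4.6 down to 48/52 = 0.9 person-years. With zero events, the exact two-sided 95% Poisson upper limit is then 3.69/4.6 = 0.8 to 3.69/0.92 = 4.0 per person-year.

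Most of this stands as a limit on severity. It does not supply the missing denominator, window or period split. The first-part wording in section 13.4 also does not settle the through-week-13 wording in section 11.13.1.

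A reader might go further and infer that following non-responders off drug dilutes on-drug harm. The documents do not support a fixed direction. Extra follow-up can only add subjects to an ever-had-an-event percentage; a lower pooled figure comes from short exposure among those counted. A reader might also compute, for a placebo-first non-responder, that a true rate ratio of 2 shrinks to (2 × 12 + 1 × 24)/36 = 1.33. That is a person-time ratio, not a percentage, and it assumes no carry-over. Section 1.1.3 reports eosinophil suppression for 57 to 239 days in an asthma study.

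**Conclusion.** The point holds as a gap in the safety analysis. Section 13.3 gives no way to read a long-term AE percentage against time on drug, while scheduled time on drug varies 4-fold by week 48. Under an assumed constant rate of 0.5 per person-year and no drug effect, that alone moves the percentage from 10.9% to 37.0%; the low and high assumed rates give 2.3% to 8.8% and 20.6% to 60.3%. These figures illustrate the size and do not predict this trial's AE rate. A spread of several years would follow only if AEs are recorded in the extension, on which sections 11.2 and 6.5 disagree.

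The week-13 cut is a separate defect. First-dose reactions in the placebo arm could be counted under placebo; the text does not say that they will be.

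Neither issue touches the primary efficacy test. The change is worth making because it is cheap and because one subject is 10 percentage points of an arm.

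**What to change.** 1. **Randomised comparison.** Keep percentages of subjects by arm, and cut AE data immediately before the week-12 dose. Align sections 11.13.1 and 13.4 with this.
2. **First active dose.** Report reactions after the first active dose as a percentage of subjects, for both arms (week 0 for benralizumab, week 12 for placebo). Per-subject risk is the natural scale for these events.
3. **Long-term safety.** Alongside percentages, report AEs and SAEs as events per person-year with exact Poisson intervals. State person-years in each column, with separate columns for placebo, early active, later active and after-last-dose time. Define treatment-emergent and a stated post-dose window for on-drug time, with a longer-window sensitivity analysis because of carry-over.
4. **Interpretation.** State that on-drug versus off-drug contrasts are descriptive. They are confounded by response status and by 4-weekly versus 12-weekly contact, and rates do not remove this.
5. **Recording period.** Reconcile section 11.2 with section 6.5 and Appendix B on whether AEs are recorded after the first year.

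The cost is analysis wording and a few extra tables from dose and AE records already collected; no dose, visit or data item changes. The rates assume a roughly constant hazard within each band and will be imprecise with 20 subjects.

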Study MI-CP166, a multicenter, double-blind placebo controlled study in 27 subjects with eosinophilic asthma, examined the effect of single dose iv or multiple dose sc benralizumab on eosinophil counts in airway mucosa/submucosa, sputum, bone marrow and peripheral blood (11). In cohort 1, intravenous benralizumab produced a median decrease from baseline of 61.9% in airway mucosal eosinophil counts (Day 28; placebo: +19.6%; P = .28), as well as an 18.7% decrease (Day 21) in sputum and a 100% decrease (Day 28) in blood counts. Eosinophils were not detectable in bone marrow of benralizumab-treated subjects (Day 28, n = 4). In cohort 2 sc benralizumab demonstrated a combined (100 + 200 mg) median reduction of 95.8% in airway eosinophil counts (Day 84; placebo, 46.7%; P = .06), as well as an 89.9% decrease (Day 28) in sputum and a 100% decrease (Day 84) in blood counts.

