### **3.2.2 Secondary Endpoints**

Secondary endpoints include: 1) Reduction in AEC at 12 weeks, 2) Frequency and severity of AEs, 3) Reduction in signs and symptoms of HES, 4) Tissue eosinophilia, 5) Numbers of eosinophils, mast cells and their precursors in bone marrow, 6) Levels of markers of eosinophil and mast cell activation, 7) Eosinophil count and background HES therapy at the 48 week visit, 8) PK and ADA levels, 8) Eosinophil count after 24 weeks of every 8 week dosing.

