### **6.3 Randomization and Blinding**

The subjects, the investigators, and all who are involved in the evaluation of the study subjects including study monitors and central laboratory personnel are blinded to a subject's treatment assignment until all subjects have completed the week 13 visit. The NIH research pharmacist is identified as the unblinded third party who will be in charge of treatment assignment, maintaining study supplies/inventory list, and preparing the blinded study medication for each subject. The NIH research pharmacist will be independent of any study assessments. To maintain blinding, any discussion of the treatment assignment between the clinicians and the pharmacy staff is prohibited until the study is unblinded.

Subjects will be assigned a screening number after completion of the eligibility checklist for enrollment in the study in CRIMSON. The study statistician or NIH research pharmacist will generate the randomization codes. These codes will be maintained by the NIH research pharmacist. To reduce the potential for participant dropouts during the period between enrollment and initial dosing of the study agent, randomization will be defined to occur on the day that the first dose of study drug is administered. A study allocation number (1 through 20) will be assigned at this time.

Because benralizumab (but not placebo) is expected to decrease peripheral and bone marrow eosinophil counts, the results of white blood cell count, peripheral eosinophil count, lymphocyte phenotyping, and bone marrow aspirate and biopsy collected after the initial dose of benralizumab or placebo until week 13 of study treatment will be blinded to the study team and subjects until all subjects have completed week 13 of the study. Results of blood tests performed after this time (week 13 until the end of the study) will not be blinded since all subjects will be receiving benralizumab and knowledge of the results would not allow the study team to determine whether the subject had received benralizumab or placebo during the double-blind portion of the study. The NIH Clinical Research Information System (CRIS) by which laboratory

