### 2) Basophil, mast cell and eosinophil precursors

- Basophils: Due to the low numbers of circulating basophils in peripheral blood, basophil numbers and activation will be assessed by whole blood flow cytometry using CCR3 and CD203c, a specific marker of basophil activation.

- Mast cells: Mast cells will be quantified and assessed for spindle-shape (activation) in bone marrow biopsy specimens stained for tryptase and CD117 before and during benralizumab therapy. Flow cytometry of the aspirate specimens will be used to assess surface markers of activation (CD2 and CD25). Serum tryptase levels will also be assessed.
- Eosinophil precursors: Eosinophil precursors will be assessed morphologically and by flow cytometry using antibodies to IL-5R and CD34 before and after 12 weeks of benralizumab therapy.

3) Predictors of response/resistance to benralizumab

- Prior studies have shown a correlation between decreased IL-5R levels on the surface of eosinophils and increased soluble IL-5R levels in serum (7). Consequently, surface expression of IL-5R will be quantified by whole blood flow of eosinophils using Quantibrite beads and soluble IL-5R will be measured by ELISA before and at 12, 24, 36 and 48 weeks of benralizumab therapy.
- The presence of anti-drug antibodies will be assessed before and at specified time points during the study. Drug levels will also be assessed.

4) Immunologic consequences of benralizumab therapy

Activated eosinophils are a source of a wide variety of cytokines, chemokines, and other mediators. Thus, depletion of eosinophils in patients with HES is likely to have secondary effects on other immune cells. Whole blood flow cytometry will be performed at baseline and every 12 weeks on benralizumab therapy to look at T/B/NK cell numbers, activation status and cytokine production. In addition, PBMC will be purified from whole blood at the same time points for generation of supernatants for cytokine analyses by suspension array in multiplex and isolation of RNA for microarray and/or RNAseq analysis.

- In view of murine studies demonstrating that eosinophil-deficient mice have decreased plasma cells and impaired responses to secondary immunization with T cell dependent antigens (12), plasma cells will be quantified in the bone marrow prior to and after 12 weeks of benralizumab therapy. In addition, anti-tetanus antibody responses will be assessed in all subjects at week 28 (6 weeks following immunization).

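### Unless its denominator excludes eosinophils, the between-arm comparison of % marrow myeloid precursors in 13.3 mixes eosinophil clearance with any real effect on precursors

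*Combined protocol and SAP*

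**What the plan says.** Section 3.2.2 (and the Protocol Summary) lists as a secondary endpoint "Numbers of eosinophils, mast cells and their precursors in bone marrow". No unit is attached.

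Section 13.3 covers the continuous secondary endpoints that measure change from baseline to week 12. The marrow variables it names are percentages: "for example, % bone marrow eosinophils, and % bone marrow myeloid precursors". On method it says "These will be analyzed similarly to the percentage of pretreatment AEC", which means the week-12 value as a percentage of the baseline value. For that variable "we use a Wilcoxon-Mann-Whitney test".

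On the expected drug effect, Section 6.3 says "Because benralizumab (but not placebo) is expected to decrease peripheral and bone marrow eosinophil counts". Section 1.1.3, on an earlier asthma study, says "Eosinophils were not detectable in bone marrow of benralizumab-treated subjects (Day 28, n = 4".

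Appendix D describes the other marrow measures. For mast cells: "Mast cells will be quantified and assessed for spindle-shape (activation) in bone marrow biopsy specimens stained for tryptase and CD117". For plasma cells: "plasma cells will be quantified in the bone marrow prior to and after 12 weeks of benralizumab therapy". Neither has a unit, and plasma cells are not in the list of secondary endpoints. Nowhere do the documents give a denominator for the marrow percentages, a conversion to counts or an adjustment for cellularity.

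**The concern.** A percentage of all marrow cells depends on every lineage in its denominator. Here one of those lineages is the drug's target and is expected to fall sharply on benralizumab and not on placebo. The percentage of any other lineage then rises in the active arm even if not one of its cells has changed. Baseline balance does not help, because the shift is produced by treatment after randomisation.

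The variable exposed in the text is the myeloid precursor percentage. A significant rise could be read as a drug effect on precursors when it reflects only a smaller denominator, and a real fall could be hidden. Secondary objective 3 asks about effects on marrow eosinophils, mast cells and their precursors, so this comparison is meant to carry information about cells beyond mature eosinophils.

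**Working it through.** **Plan's own figures.** The documents give no power or sample size for the marrow endpoint. The only power figures are in Table 2 for the primary Fisher test. They reproduce (1% v 60% responders, 10 per arm: 79.0%) and are not touched by this point.

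**Inputs from the documents.** 10 per arm (13.2); two-sided 5% level for all tests (13.4); Wilcoxon-Mann-Whitney on the ratio to baseline (13.3); marrow eosinophils fall in one arm only (6.3).

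**Inputs assumed.** Baseline marrow eosinophil fraction e = 10% to 40%; SD of the log week-12/baseline ratio 0.3 or 0.5; full clearance (d = 1); a denominator of all nucleated cells. None of these is in the documents.

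**Formula.** Let eosinophils be a fraction e of counted cells and let a share d of them be removed, with other counts unchanged. The total becomes (1 - e·d) of its former size, so another lineage's percentage is multiplied by 1/(1 - e·d). If a small lineage really falls by a fraction f, its observed ratio is (1 - f)/(1 - e·d).

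**Illustration.** Take 1,000 cells: 300 eosinophils, 100 precursors, 600 others. Precursors are 100/1,000 = 10.0%. Remove the eosinophils and they are 100/700 = 14.3%, a ratio of 1.43 with no precursor gained. Excluding eosinophils from the denominator gives 100 × 10.0/(100 - 30) = 14.3% before and 100 × 14.3/(100 - 0) = 14.3% after, a ratio of 1.00.

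**Size with 10 per arm** (simulated log-normal ratios, exact two-sided test). Rates are for SD 0.3, with SD 0.5 in brackets.

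| e | Shift 1/(1-e) | False increase, no true change | Real 30% fall detected |
|---|---|---|---|
| 0 (no dilution) | 1.00 | nominal | 65% (29%) |
| 10% | 1.11 | 11% (7%) | 37% (16%) |
| 20% | 1.25 | 32% (13%) | 12% (6%) |
| 30% | 1.43 | 64% (30%) | see below |
| 40% | 1.67 | 89% (54%) | see below |

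At e = 30% a 30% fall cancels exactly, 0.70/0.70 = 1.00, so the test can reject only at about its own error rate. At e = 40% the same fall appears as a rise, 0.70/0.60 = 1.17. Separate runs with different spreads of e between subjects agree with the table to within about four percentage points.

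**If precursors include eosinophil precursors.** Section 1.2 expects these to fall. If a share g of the counted precursors is cleared, the ratio is about (1 - g)/(1 - e). At e = 20% this is 0.90/0.80 = 1.13 for g = 10%, 1.00 for g = 20% and 0.70/0.80 = 0.88 for g = 30%. The direction depends on whether g exceeds e, and the documents give neither.

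**Eosinophil percentage itself.** A real 90% fall shows as 0.10/(1 - 0.9 × 0.10) = 0.110 at e = 10% (an 89% fall) and 0.10/(1 - 0.9 × 0.30) = 0.137 at e = 30% (an 86% fall). At full clearance there is no distortion.

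**The case against.** The strongest reply is that the plan says less than a critic might read into it.

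- The percentages in 13.3 are introduced as examples. A reader might infer that all marrow lineages, including mast cells and plasma cells, are compared as percentages and biased upward. The text does not say so. Mast cells are read on stained biopsy sections, where a count per area or field has no shared denominator. Plasma cells are an Appendix D research measure outside the endpoint. For both, the gap is an unstated unit. This part of the reply stands.
- A reader might also infer that the precursor comparison measures only eosinophil removal. That would need a denominator containing eosinophils and unchanged precursor counts. Neither is stated, and a value taken within a CD34-positive flow gate would not include mature eosinophils. This stands as a limit on the claim, but the denominator is still open.
- Full clearance rests on four asthma subjects given intravenous drug, and e and the SD are assumptions. This also stands. At e = 10% the distortion is small.
- One might add that a ratio is undefined when the baseline is zero. Nothing in the documents suggests that either named variable is zero at baseline, so no weight is put on this.
- The endpoint is secondary, and the decision on further study rests on blood AEC (13.4). That is correct and limits the consequence.

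None of this removes the central point. 13.3 names a non-eosinophil percentage and fixes its analysis without a denominator, and the expected drug effect falls on one arm.

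**Conclusion.** The concern holds in a limited form. The endpoint is worded as numbers, while the stated analysis of myeloid precursors is a percentage compared as a ratio to baseline. If the denominator is all nucleated marrow cells, eosinophil clearance shifts an unchanged non-eosinophil lineage by about 1/(1-e) in the benralizumab arm alone. The consequence runs from minor (e = 10%) to serious (e = 30% or more), and the documents do not allow it to be placed within that range. If eosinophil precursors are counted among the myeloid precursors, a real fall and an artefactual rise are mixed and the net direction cannot be predicted.

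The percentage of marrow eosinophils and the primary AEC endpoint are not materially affected. The documents do not support a finding of bias in the mast-cell or plasma-cell results. The point is worth correcting because a better measure is available at almost no cost.

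**What to change.** In 13.3, and aligned with 3.2.2:

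1. Keep the eosinophil percentage for eosinophils.
2. Define myeloid precursors and say whether eosinophil precursors are included. Analyse non-eosinophil myeloid precursors as a percentage of non-eosinophil nucleated cells, 100 × precursor % / (100 - eosinophil %), from the same differential at baseline and at week 12. Any eosinophil precursors removed from the numerator should be removed from the denominator too. Keep the Wilcoxon-Mann-Whitney test on the ratio to baseline.
3. Report the all-cell percentage as a supporting analysis.
4. State the unit for mast cells, and for plasma cells if they are compared: either the biopsy-section count, shown with cellularity because a per-area count depends on it, or the same eosinophil-excluded percentage. Do not use a percentage of all marrow cells.

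Fix these choices before marrow results are examined by arm. If that has already happened, label the analysis as post hoc.

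The cost is some wording and one extra derived variable with slightly noisier values. The precursor formula uses the two percentages 13.3 already names, provided they come from the same differential. No new biopsy or reader is needed.
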